There were no serious device-related adverse events reported in the trial. Two (2) SAEs were reported, neither of which was related to the study device, a fractured fibula and flu symptoms requiring hospitalization. Among the 117 subjects in the Safety Cohort, 93 AEs in 61 subjects were reported as device-related / possibly device-related, and another 26 AEs were reported in 21 subjects as not / unlikely device-related. All device-related AEs were mild (78%) or moderate (22%) and none required any significant intervention (defined as "intervention to prevent permanent impairment / damage" per the AE CRF). No device-related AEs required surgical treatment to resolve, and only 2

required medical intervention: topical vaginal estrogen for vaginal erythema and a topical antifungal for yeast infection. Modification to pre-existing Estrace usage was also required in some subjects.

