4.2 Adverse Event Association

The relationship of all AEs to the Eclipse System will be reported on the Case Report Forms by the site investigator according to the definitions provided in **Table 6**. Any devices associated with SAEs will be returned in order to facilitate product investigations. Devices associated with non-serious adverse events may also be returned, at the direction of the Sponsor, to assist with product investigations.

Table 6. Adverse Event Relationship to Device

Term	Definition
Definite	Adverse event whose timing is highly plausible for causality and which cannot be explained by other factors
Probable	Adverse event whose timing is reasonable for causality and is unlikely to be explained by other factors
Unlikely	Adverse event whose timing is unlikely for causality and which could be explained by other factors
Not related	Adverse event whose timing makes causality improbable and which could easily be explained by other factors
Unknown	Adverse event whose plausibility of timing cannot be judged or in which information regarding other factors does not exist

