12 SAFETY AND TOLERABILITY

12.1 Adverse Events

All adverse events (AEs) occurring after a subject has been fit with the Eclipse System, at the Initial Fitting Visit, will be recorded. All AEs will be coded into system organ class and preferred term using MedDRA v17.0.

The Clinical Events Committee (CEC) will review all AEs at regular intervals to confirm MedDRA classification and determine the relationship to the study device (not related, unlikely, probable, definite, or unknown). Where appropriate, relationship to the study device will be further classified by component (Eclipse insert, trial insert, sizer, pump, valve, extension tube, regulator). For a more detailed description of the AE review/adjudication and MedDRA coding processes, please refer to the CEC Charter ver. 2.0.

The incidence of adverse events will be summarized by system organ class and preferred term. Subjects will be counted at most one time per system organ class and at most one time per preferred term. For summaries by severity, subjects will be counted at most one time per system organ class and at most one time per preferred term, at the highest recorded severity.

The following summaries will be provided:

- AEs per time period (e.g. fitting vs. treatment)
- AEs related to study device (defined as those categorized by the CEC as being probably or definitely related to study device)
- Serious adverse events (SAEs; if applicable)
- AEs leading to withdrawal from the study
- AEs by severity
- AEs related to study device, by severity

An additional summary of TEAEs, by preferred term, sorted by descending overall frequency, will also be presented.

Data listings, including system organ class and preferred term, will be provided for all AEs, all SAEs, and all AEs related to study device.

Separate listings will be provided for all adjudicated events, and will include all information provided by the CEC.

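### The relatedness scale has no level for plausible timing with another possible cause, and the SAP leaves events adjudicated Unknown out of the device-related count, which may therefore be understated

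*SAP*

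**What the plan says.** Protocol 3.5 makes the number of CEC-adjudicated device-related AEs and device-related SAEs the only safety endpoint. Neither that section nor Protocol 3.10 says which relatedness levels count as device-related.

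Protocol 4.2, Table 6, defines five levels:

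- Two levels point to the device. For Probable the table asks for this: "Adverse event whose timing is reasonable for causality and is unlikely to be explained by other factors". Definite is the stricter form, with a stronger fit in time and every other cause excluded.
- Two levels point away from it. The table words the Unlikely level as follows: "Adverse event whose timing is unlikely for causality and which could be explained by other factors". Not related is the stricter form, with a poorer fit in time and an easy alternative explanation.
- The fifth level, Unknown, is kept for cases that cannot be assessed, in these words: "Adverse event whose plausibility of timing cannot be judged or in which information regarding other factors does not exist".

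SAP 12.1 gives the CEC the same five levels; it is to "determine the relationship to the study device (not related, unlikely, probable, definite, or unknown". The counting rule is in the same section: "AEs related to study device (defined as those categorized by the CEC as being probably or definitely related to study device". For the details of adjudication, SAP 6.5 and 12.1 refer to a CEC Charter that is not among the documents.

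For the earlier LIFE study, Protocol 1.6.2 groups the events differently: "93 AEs in 61 subjects were reported as device-related / possibly device-related". A further 26 AEs in 21 subjects were called not or unlikely related. The LIFE Safety Cohort had 117 subjects.

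**The concern.** Each level in Table 6, apart from Unknown, combines two judgements: whether the timing fits, and whether something else could explain the event. Events where the timing fits and something else could also explain them are foreseeable here. Protocol section 6 lists yeast infection, lower urinary tract infection, spotting and discharge among the anticipated risks. Protocol 2.6.2 allows women with treated atrophy or a treated positive urine test to go on to fitting. The documents do not say how often such mixed events occur.

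If the scale has no place for them, their classification depends on the habits of individual adjudicators. If the counting rule also drops the undetermined events, the endpoint takes in only events where another cause was judged unlikely or excluded. The study has a single arm, so no control rate would show whether attribution had been too strict. A reader who sets the result beside LIFE could take a difference in definition for a difference in safety.

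**Working it through.** **Step 1: cross the two judgements in Table 6.**

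| Timing | Other cause excluded or unlikely | Other cause possible |
|---|---|---|
| Plausible | Definite, Probable | no level |
| Implausible | no level | Unlikely, Not related |

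Unknown lies outside the grid. It needs timing that cannot be judged, or an absence of information on other factors.

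Take an event with reasonable timing and an identified alternative cause. It fails Definite and Probable because the other cause is not unlikely. It fails Unlikely and Not related because the timing does fit. It fails Unknown because the timing can be judged and the information exists. It meets none of the five definitions. (The opposite corner is empty too, but nothing here depends on it.)

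**Step 2: apply the counting rule in SAP 12.1.**

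- Present count = Definite + Probable.
- Count of everything not judged Unlikely or Not related = Definite + Probable + Unknown.
- If gap events are also to count, shortfall = Unknown (including any gap events placed there) + gap events placed in Unlikely or Not related.

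The first term is lost by rule. The second depends on the adjudicators: it is zero if they move every gap event up to Probable, and equals all gap events if they move every one down to Unlikely. The documents give no expected number for either term, so the shortfall cannot be computed.

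**Step 3: the LIFE figures (Protocol 1.6.2).**

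- All AEs: 93 + 26 = 119.
- Related or possibly related: 93/119 = 78.2% of AEs.
- Subjects with such an event: 61/117 = 52.1% (exact 95% CI 42.7% to 61.5%).

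The documents do not divide the 93 into related and possibly related. To show how much the unknown split matters, let s be the share that were only possibly related, and suppose that none of those would count under a probable-plus-definite rule. Both are assumptions. The remaining count is 93 × (1 − s):

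| s (assumed) | Events still counted |
|---|---|
| 0 | 93 |
| 0.10 | 83.7 |
| 0.25 | 69.8 |
| 0.50 | 46.5 |
| 0.75 | 23.3 |

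The effect runs from none to most of the count. The table shows sensitivity to an unknown; it does not estimate what will happen in LIBERATE.

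**The case against.** The best reply has four parts.

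*Direction.* A reader might infer that gap events must go to Unlikely or Unknown, so that doubt always favours the device and the endpoint is understated as a matter of fact. The definitions do not support this. A gap event fails Unlikely and Unknown just as it fails Probable, and an adjudicator who weighs timing first could well choose Probable. For gap events the documents show an ambiguity without a direction. The reply stands, but it does not reach the exclusion of Unknown, which is fixed by the SAP.

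*The unseen Charter.* The CEC Charter may contain a tie-break, and Protocol 4.3.3 lets the medical monitor ask for more information before relatedness is decided. Either could shrink the problem. A tie-break for gap events would not by itself change the SAP's treatment of Unknown.

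*LIFE.* A reader might infer that the trial sets out to show durable safety relative to LIFE and uses a narrower definition to do so. The stated objective (Protocol synopsis and 3.1, SAP 5.1) is durability after 3 and 12 months of use. Similarity to LIFE is only an expectation in the rationale (Protocol 1.7), and no formal comparison is planned. LIFE's levels are not defined either, so its possibly related events might correspond to Probable here. What stands is that the two counts are worded differently and that the mapping between them is unknown.

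*Visibility.* SAP 12.1 also summarises AEs without restriction to related ones (by period, by severity and by preferred term). It lists all AEs, and separately lists all adjudicated events with everything the CEC provided. Events outside the count can therefore be found and recounted. That is a real mitigation, but a listing is not the endpoint.

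**Conclusion.** The concern holds as a risk to the device-related count, not as a demonstrated bias. Two things are certain from the text: Table 6 and SAP 12.1 have no level for plausible timing with a possible alternative cause, and events adjudicated Unknown are outside the device-related count by rule. Whether gap events are lost depends on adjudication practice and on a Charter not available here. The understatement could be nil or large, and no figure can be given. It would affect the device-related AE and SAE counts; overall AE reporting is not affected. The LIFE figure of 52% of women should not be placed next to the LIBERATE figure without a row on a matching definition.

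**What to change.** In SAP 12.1:

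1. Count as device-related every AE and SAE that the CEC did not judge Unlikely or Not related, that is, Definite, Probable and Unknown. Keep probable plus definite as a separate row. The first row is the closer match to the LIFE wording and can serve as the bridging row, with a note that LIFE's levels are not defined in these documents.
2. State that an event with plausible timing and a possible alternative cause counts as device-related, preferably through a Possible level on the CEC adjudication form. Item 1 alone would miss gap events already placed in Unlikely.
3. If adjudication has begun, have the CEC re-read the Probable, Unlikely and Unknown events against the new level. Including Probable keeps the exercise even-handed, because events stretched upward are then re-examined as well.

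The cost is a somewhat less favourable device-related rate, a change of SAP wording and a short CEC re-review. No new patient data are needed. If Table 6 itself is changed, a protocol revision and a CRF change follow, because investigators rate events on the same scale; confining the new level to CEC adjudication avoids that.
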